9.4.3 ANALYSIS OF THE SECONDARY ENDPOINT(S)

The secondary endpoints will be tested using a two-sided alpha of 0.05; no multiplicity adjustment is planned, and p-values will be nominal. Secondary endpoint analyses will use the ITT population.

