Objective: To evaluate the efficacy of IXT-m200 in increasing the number of participants	Endpoints: Responders at Week 25 as measured by the DSM-5 criteria. A responder is a participant who meets the definition of early remission, i.e., ≥3 months and <12 months without meeting DSM-5 criteria, while disregarding the result for craving.	
achieving early remission.	Clinical Question: Does adding IXT-m200 to standardized CBT program improve the proportion of participants achieving early remission, relative to the CBT program alone in treatment-seeking participants regardless of IXT-m200 interruption or discontinuation, for any reason?	
	Estimand: The difference in the proportion of responders between the IXT-m200 and placebo groups, where a responder is a participant who meets the definition of early remission, i.e., ≥3 months and <12 months without meeting DSM-5 criteria, other than craving. All observations will be used, regardless of whether a participant discontinued treatment early. All missing values will be imputed assuming the participant has not achieved early remission.	
Objective: To evaluate the efficacy of IXT-m200 in improving	Endpoints: Difference between groups in Clinical Global Impression of Change (CGIC) at Week 13, 25, and Week 33.	

clinician-rated response to treatment.	Clinical Question: Does adding IXT-m200 to standardized CBT program improve CGIC at Week 13, 25, and Week 33, relative to the CBT program alone in treatment-seeking participants regardless of IXT-m200 interruption or discontinuation, for any reason? Estimand: The difference in CGIC at Week 13, 25, and Week 33, between the IXT-m200 and placebo groups in treatment-seeking individuals with MUD. All observations will be used, regardless of whether a participant discontinued treatment early. Missing values will not be imputed.

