2.4.1. Data Safety Monitoring Board

The DSMB will review an interim analysis report after the last participant in Cohort 1 has available Week 25 data (or has previously discontinued) at which time the DSMB will review efficacy in addition to the typical safety report content. On the basis of the Week 25 interim analysis, the DSMB may recommend whether to proceed to Cohort 2, and if proceeding, which dose to use for the IXT-m200 group (e.g., escalate to 3.0 g, continue at 1.5 g, or reduce). If the DSMB recommends continuing dosing at 1.5 g in Cohort 2, a sample size recalculation will be executed using the pooled standard deviation of the primary endpoint in Cohort 1. The DSMB may also recommend that the study be stopped early if there is sufficient evidence that any of the following circumstances apply.

- Determination of unexpected, significant, or unacceptable risk to participants either related to the study intervention or unrelated events (such as a national health emergency);
- Demonstration of efficacy that would warrant early termination;
- Insufficient compliance to protocol requirements;
- Data that are not sufficiently complete and/or evaluable;
- Determination that the primary endpoint has been met;
- Determination of futility.

The Sponsor will make the ultimate decision as to whether to accept the DSMB's recommendation. The Sponsor may have access to group-level data but will not have access to unblinded participant-level data at the time of the interim analysis. The Sponsor will have ongoing access to blinded individual participant data from saliva tests and daily self-reported drug use surveys. Participants will continue the study in Cohort 1 through Week 33 while the interim analysis is ongoing.

3. Analysis Sets

For the purposes of analysis, the following analysis sets are defined:

Table 5 Analysis Populations

Participant Analysis Set	Description						
Intent-to-treat (ITT)	The intent-to-treat (ITT) population will be comprised of all randomized participants categorized by their randomized treatment assignment.						
Modified intent-to-treat (mITT)	The modified ITT (mITT) population will be comprised of all randomized participants who received at least one dose of study drug. Participants will be analyzed according to their randomized treatment assignment.						

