4.1.2. Other Missing Data, and Data Errors

Any missing values for treatment responder endpoints will be imputed as "non-responder." Missing values for global impressions scales will be imputed as the neutral result of "No Change."

For endpoints related to saliva screens or self-report surveys, if a participant withdraws from the study, all remaining days following withdrawal will be imputed as not abstinent.

Missing values for quality of life, as measured by the Treatment Effectiveness Assessment, will not be imputed. Participants who withdraw or discontinue prior to Week 5, or do not have any reported saliva or self-report use data between Weeks 5 and 25 will not be included in the analysis.

In general, missing and partial dates will be displayed as captured in participant listing displays. For adverse events:

- Missing start day: first of the month will be used unless this is before the start date of study drug; if the partial date is the same month as the first dose of study drug, the treatment start day will be used and the event will be considered treatment-emergent.
- Missing stop day: the last day of the month will be used.
- Completely missing start or end dates will remain missing, with no imputation applied. Time to onset will be missing, and duration will be considered ongoing.

For concomitant medications/medical history:

- If the partial date is a start date, January and 1 will be used for a missing month and missing day, respectively.
- If the partial date is a stop date, December will be used for a missing month, and the end of the month will be used for a missing day (i.e., 28/29/30/31 dependent on the month and year of the partial date).

For pharmacokinetic purposes, missing concentration data will be considered as non-informative and will not be imputed. No concentration estimates will be provided for missing sample values.

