4.7.1.2. Main analytical approaches

All secondary analyses will use the ITT population.

Quality of life analysis

A secondary objective is to evaluate the efficacy of IXT-m200 in improving patient-rated quality of life, as measured by change from screening in the Treatment Effectiveness Assessment score at Week 13, Week 25, and Week 33.

The Treatment Effectiveness Assessment includes four items with 10 ordinal response options ranging from "not well at all" to "extremely well" (Likert scale), where higher values indicate better quality of life. The Treatment Effectiveness Assessment score is the sum of the four responses (minimum = 4, maximum = 40); the Treatment Effectiveness Assessment score will not be computed if the participant did not respond to all four items.

As the sum of four ordinal items, a nonparametric approach to the analysis will be used since it is unlikely the values will meet the necessary normality assumptions for MMRM or ANCOVA

methods. Therefore, the change from screening in Treatment Effectiveness Assessment score at each post-screening timepoint will be compared in each IXT-m200 group versus the placebo group using a Kruskal-Wallis test.

For each comparison and timepoint, the Hodges-Lehmann estimate and 95% confidence intervals for the difference in group medians, and two-sided p-values will be reported.

A waterfall plot, depicting the median change from baseline at each timepoint will be provided for each treatment group. Pseudo-R code for the plot is included in Exhibit 4. Exhibit 5 contains an example of the waterfall plot.

[figure not shown]
Exhibit 4 Pseudo-R Code for TEA Waterfall Plot

```
coltrt <- ifelse(medstrt >= 0,rgb(0.2,0.7,0.9,.75), rgb(1,0.5,0,.75))
colplcbo <- ifelse(medsplcbo >= 0,rgb(0.2,0.7,0.9,.75), rgb(1,0.5,0,.75))

par(mfrow=c(1,2))
barplot(medstrt,ylim=c(min(c(medstrt,medsplcbo)),max(c(medstrt,medsplcbo))),col=coltrt,yla
b="Change from Baseline")
segments(x0=0,x1=4,y0=0,y1=0,lty="dashed")

title('Change from Baseline in TEA Score for IXT-m200 Group')
axis(1, at=1:3, labels=c("Week 13","Week 25", "Week 33"))
barplot(medsplcbo,ylim=c(min(c(medstrt,medsplcbo)),max(c(medstrt,medsplcbo))),col=colplc bo)
title('Change from Baseline in TEA Score for Placebo Group')
axis(1, at=1:3, labels=c("Week 13","Week 25", "Week 33"))
segments(x0=0,x1=4,y0=0,y1=0,lty="dashed")
```

Exhibit 5 TEA Waterfall Plot

Proportion of responders meeting early remission criteria

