A secondary objective is the proportion of responders at Week 25 as measured by DSM-5 criteria. A responder is a participant who meets the definition of early remission, i.e., ≥3 months and <12 months without meeting DSM-5 criteria, while disregarding the result for craving. All other criteria, 10 in total, will be counted. Participants that withdraw or discontinue prior to Week 5, or do not have any reported saliva or self-report use data between Weeks 5 and 25 will not be included in the analysis.

The proportion of participants achieving a response will be compared in each IXT-m200 dose group versus the placebo group using a stratified Mantel-Haenszel statistic with stratification level of past-month METH use at screening (discrete). The output will provide the risk difference between each IXT-m200 dose group and the placebo group, two-sided p-values, and 95% confidence intervals using the Miettinen-Nurminen (score) confidence limits⁴.

Clinician-rated response to treatment

A secondary objective is to evaluate the efficacy of IXT-m200 in improving clinician-rated response to treatment, as measured by Clinical Global Impression of Change (CGIC) at Week 13, 25, and Week 33. The CGIC is completed by the clinician and has seven ordinal responses (Likert scale) ranging from "very much improved" to "very much worse". The comparison between groups will be conducted using a nonparametric Kruskal-Wallis test. The percentage of subjects in each scale category will be tabulated by treatment group and timepoint, and a graphical display using a frequency polygon will be produced for the Week 25 values.

Patient-rated response to treatment

Another secondary objective is to evaluate the efficacy of IXT-m200 in improving patient-rated response to treatment as measured by the Patient Global Impression of Change (PGIC) at Week 13, 25, and Week 33. PGIC is completed by the patient and has seven ordinal responses (Likert scale) ranging from "very much improved" to "very much worse".

The comparison between groups will be conducted using a nonparametric Kruskal-Wallis test. The percentage of subjects in each scale category will be tabulated by treatment group and timepoint, and a graphical display using a frequency polygon will be produced for the Week 25 values.

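### The Week 25 early-remission analysis drops randomised participants whom the SAP's own ITT set and estimand count as not in remission

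*SAP*

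**What the plan says.** **The exclusion.** In SAP section 4.7.1.2, under the early-remission heading, "Participants that withdraw or discontinue prior to Week 5, or do not have any reported saliva or self-report use data" in Weeks 5 to 25 are removed from the Week 25 comparison.

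**The rules it meets.**
- Earlier in the same section: "All secondary analyses will use the ITT population".
- SAP section 3, Table 5: the ITT "population will be comprised of all randomized participants categorized by their randomized treatment assignment".
- The estimand for this endpoint (SAP section 1.1, Table 2): "All observations will be used, regardless of whether a participant discontinued treatment early", and "All missing values will be imputed assuming the participant has not achieved early remission".
- SAP section 4.1.2: "Any missing values for treatment responder endpoints will be imputed as" non-responder.
- Protocol 9.4.3: "Secondary endpoint analyses will use the ITT population". Protocol 9.4.3.1, which describes this analysis, contains no exclusion. SAP section 4.13 nevertheless declares no departures from the protocol's analyses.

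**Where else it appears.** SAP section 4.8 repeats the sentence for Week 33 remission and for complete abstinence in Weeks 21 to 25. It uses a saliva-only version for sequential weeks of abstinence. Section 4.1.2 also has it ("Participants who withdraw or discontinue prior to Week 5, or do not have any reported saliva or self-report use data"), directly after the rule for the Treatment Effectiveness Assessment (TEA) and with no endpoint named.

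**The concern.** One randomised participant has two different statuses. Someone who leaves in Week 3 has no Week 25 checklist. Table 2 and section 4.1.2 put that person in the denominator as a non-responder; section 4.7.1.2 takes the person out. Two careful programmers could report different denominators, proportions and p-values.

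The excluded group is defined by what happens after randomisation, so removing it can break the comparability of the arms.

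The rule could also delete outcomes that were observed. Section 4.7.1.2 does not define *discontinue*. In Protocol 7.2 a discontinued participant has stopped study drug but stays in the assessments, and the dose-discontinued schedule (Protocol 1.3.3) still has the DSM-5 assessment on Day 169. The outcome is a DSM-5 checklist (Protocol 8.1.4), so a lack of saliva or app data does not make it missing.

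**Working it through.** **Plan figures.** The plan gives no remission rate, power figure or early-loss rate for this endpoint. SAP Table 4 concerns the primary endpoint. Its detectable differences for 40 versus 20 (0.78, 0.84 and 0.90 SD) reproduce with a noncentral t as 0.780, 0.835 and 0.903, but this point does not rest on them. The dropout figure of up to 50% in SAP section 2.2 is not the excluded share, because the rule keeps people who leave after Week 5 with some use data.

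**Inputs.** Planned Cohort 1 is 40 active and 20 placebo (SAP sections 1.2 and 2.2). Section 1.2 states that the study stopped before Cohort 2 enrolled. The test is two-sided at 5%, nominal. All response and exclusion rates below are assumptions.

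**Formulas.** Let R be the responders, x the number excluded and o the observed responders among them, with a for active and p for placebo.
- ITT difference = Ra/40 − Rp/20
- Difference under the exclusion = (Ra − oa)/(40 − xa) − (Rp − op)/(20 − xp)

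**Case 1: no observed responder is excluded (o = 0).** An equal fraction e removed from each arm multiplies the risk difference by 1/(1 − e): 1.05, 1.11, 1.25 and 1.43 at 5, 10, 20 and 30%. A zero difference stays at zero. Unequal removal can create a difference.

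| Responders (ITT) | Excluded | ITT difference | After exclusion |
|---|---|---|---|
| 14/40 vs 4/20 | 8 and 4 | +15.0 | 14/32 − 4/16 = +18.8 |
| 12/40 vs 6/20 | 12 and 2 | 0 | 12/28 − 6/18 = +9.5 |
| 12/40 vs 6/20 | 8 and 2 | 0 | 12/32 − 6/18 = +4.2 |
| 12/40 vs 6/20 | 4 and 4 | 0 | 12/36 − 6/16 = −4.2 |

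**Case 2: an observed responder is excluded.** Start from 12/40 versus 6/20 and exclude 10% of each arm (4 and 2).
- One placebo responder among them: 12/36 − 5/18 = +5.6 points.
- One active responder instead: 11/36 − 6/18 = −2.8 points.

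**Rejection when ITT response is equal in the arms (case 1).** These come from exact binomial enumeration of the unstratified pooled score test. Analysed sizes are 40(1 − ea) and 20(1 − ep), and response among those analysed is p/(1 − e) in each arm.

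| Excluded, active/placebo | p = 10% | 20% | 30% | 40% |
|---|---|---|---|---|
| None (full ITT) | 4.0% | 4.7% | 5.1% | 5.2% |
| 20/20% | 3.9% | 5.2% | 5.3% | 5.2% |
| 30/30% | 3.8% | 5.3% | 6.1% | 6.1% |
| 20/10% | 3.4% | 5.0% | 5.5% | 6.6% |
| 10/20% | 6.4% | 5.9% | 7.1% | 7.7% |
| 30/10% | 4.3% | 6.7% | 9.2% | 12.9% |
| 10/30% | 6.7% | 8.0% | 9.9% | 13.3% |

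The SAP specifies a stratified Mantel-Haenszel analysis. A simulation of that test (two equal strata, an assumption; 200,000 runs per cell) gives the same picture: full ITT 3.5–5.2%, equal exclusion 3.7–5.1%, 30/10% 4.0–14.0%, 10/30% 6.7–13.0%.

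**The case against.** **The exclusion looks deliberate.** It recurs in several places, and a sponsor might want a set of participants observed after the grace period. But it matches no set in Table 5. Reading it as the specific rule that overrides a general one fails, because the Table 2 estimand is just as specific to this endpoint. Excluding first and then imputing among those left also fails: Table 2 covers all missing values, and early leavers are the clearest of them. The SAP's precedence over the protocol cannot settle a conflict inside the SAP. Rewriting the estimand and naming a new set would also remove the contradiction, but it would change the stated question.

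***Discontinue* may mean leaving the study.** SAP sections 1.2, 2.4 and 2.4.1 use the word for people who will have no Week 25 data. On that reading this limb deletes no observed checklist. A responder would then be lost only by attending Week 25 with no saliva result and no app entry in Weeks 5 to 25, despite twice-weekly tests and daily queries. That is possible, but nothing suggests it is common. Case 2 therefore deserves less weight than case 1.

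**The rejection rates are errors against the ITT null.** At p = 40% with 30/10% excluded, retained response is 57.1% versus 44.4%. If retained response were equal in the arms instead, rejection under the exclusion would be 3.7–5.2%, and the missing-as-failure analysis would show a 2 to 8 point difference from unequal loss alone. This is correct. The higher rates count as errors only because Table 2 makes ITT with missing as failure the target.

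**The stakes are limited.** This is one of four secondary efficacy endpoints in an exploratory study with nominal p-values, no multiplicity control and no formal stopping rules. That stands.

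**Conclusion.** The concern holds. The exclusion in SAP section 4.7.1.2 cannot be reconciled with the ITT statement in that section, with the endpoint's own estimand or with section 4.1.2. That conclusion needs no assumed rates.

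The numerical effect does need them, and its size and direction in this trial are unknown. With equal exclusion and no observed responder removed, a non-zero difference grows by 1/(1 − e), and null rejection stays at 3.8–6.1% for exclusions of 5 to 30%. Clearly unequal exclusion (30% against 10%) moved a zero difference by 9.5 points in the example, and null rejection reached about 13% at 40% ITT response. If observed responders are removed, even equal exclusion can create a difference in either direction.

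This should be corrected, but it concerns a secondary endpoint. The primary analysis has its own ITT rule without this exclusion (SAP section 4.6.1).

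**What to change.** - Delete the exclusion sentence from SAP section 4.7.1.2, from the Week 33 remission and Week 21–25 abstinence analyses in section 4.8, and from section 4.1.2.
- For these responder endpoints, keep all randomised participants in the denominator. Use any outcome observed at the endpoint visit, including from people who stop dosing but stay in the study, and score missing outcomes as non-response. TEA stays unimputed, as section 4.1.2 already says.
- For sequential weeks of abstinence, reconcile the saliva-only exclusion with the ITT statement that opens section 4.8.
- If a restricted set is wanted, present it only as a labelled supplementary analysis, define *discontinue*, and list it in section 4.13.

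**Cost.** SAP wording only, with no new data. Reported response rates will usually fall, by the factor 1 − e when no excluded participant responded: 37.5% becomes 30% at 20% excluded. They can rise where an observed responder is restored: placebo 5/18 = 27.8% becomes 6/20 = 30.0%.

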4.8. Exploratory Analyses

Exploratory analyses will be performed on the ITT population.

Proportion of responders meeting early remission criteria at Week 33

An additional exploratory objective is the proportion of responders at Week 33 as measured by DSM-5 criteria. A responder is a participant who meets the definition of early remission, i.e., \geq 3 months and \leq 12 months without meeting DSM-5 criteria, while disregarding the result for craving. All other criteria, 10 in total, will be counted. Participants that withdraw or discontinue prior to Week 5, or do not have any reported saliva or self-report use data between Weeks 5 and 25 will not be included in the analysis.

The proportion of participants achieving a response will be compared in each IXT-m200 dose group versus the placebo group using a stratified Mantel-Haenszel statistic with stratification

level of past-month METH use at screening (discrete). The output will provide the risk difference between each IXT-m200 dose group and the placebo group, two-sided p-values, and 95% confidence intervals using the Miettinen-Nurminen (score) confidence limits.

Adverse Outcomes

An exploratory objective is to evaluate the efficacy of IXT-m200 in reducing the number of adverse outcomes from the Adverse Outcome Assessment. The assessment will be conducted at Screening, and Weeks 13, 25, and 33. All responses should be counted over the past 3 months. A summary table will provided, showing the mean, standard deviation, median, and min and max for each treatment group, at each of the given weeks. No formal statistical testing will be performed for this endpoint.

Percent of days abstinent from stimulants between Week 5 and Week 25

A secondary objective is to evaluate the efficacy of IXT-m200 in preventing or reducing the relapse to stimulant use, as measured by the percent of days abstinent from stimulants following a 4-week grace period (between Week 5 and Week 25) using self-report surveys via smartphone app.

Participants are to self-report their use/abstinence for each day of the study via the smartphone app. Missing survey data will be imputed assuming a use day. The analysis will be repeated without the imputation of missing data.

The difference in percentage of days abstinent from stimulants will be compared in each IXT-m200 group versus the placebo group using a t-test. For each comparison, the point estimate and 95% confidence intervals for the difference in group means, and two-sided p-values will be reported.

A plot of all self-report survey results for each individual participant throughout the study will be provided. Pseudo-R code for the plot is included in Exhibit 6. Observations should be sorted first by the highest study day where the survey was filled out and then by the number of use days.

Exhibit 6 Pseudo-R Code for Survey Data Plot

```
par(mfrow=c(2,1))
par(mar=c(3,4,2,1))
plot(NA,NA,xlim=c(0,175),ylim=c(0,25),xlab=",
    ylab='Placebo Participant',
    main='Meth Survey Responses for Individual Subjects',yaxt='n',xaxt='n')
axis(1, at=seq(0, 175, by=7))
axis(2, at=seq(0,25,by=5))

for(i in 0:15){
    polygon(c(14*i+.5,14*i+7.5,14*i+7.5,14*i+.5), c(-5,-5,75,75),col=rgb(0,0,0,0.025),border=rgb(0,0,0,0.025))
}
```

points(nodrug_placebo\$DAY,nodrug_placebo\$SUBJIDN,col=rgb(0.2,0.7,0.9,1),pch=17,cex=1,yaxt='n') points(drug_placebo\$DAY,drug_placebo\$SUBJIDN,col=rgb(1,0.5,0,1),pch=19,cex=1)

Sequential weeks of abstinence from the end of treatment visit (Week 25)

An exploratory objective is to evaluate the efficacy of IXT-m200 in improving the length of sustained abstinence. Sequential weeks of abstinence counting backwards from the end of treatment visit (Week 25), defined as four weeks after the final planned treatment visit (Week 21), as measured by saliva screens in each IXT-m200 group will be compared to the placebo group. In the event there is no Week 25 visit, then the endpoint is counted from four weeks after the last dosing visit attended.

A "use day" or "abstinent day" will be derived as described for the primary endpoint. For each participant, sequential weeks abstinent counting backwards from the Week 25 visit will be calculated based on use/abstinent days, for a minimum of 0 weeks and maximum of 24 weeks of abstinence. Participants that withdraw or discontinue prior to Week 5, or do not have any reported saliva screen data between Weeks 5 and 25 will not be included in the analysis.

The difference between each IXT-m200 group and the placebo group in sequential weeks of abstinence counting backward from Week 25 will be estimated using an ANCOVA model. The independent variables in the model will be treatment group and stratification level of past-month METH use at screening. Adjusted means and standard errors for each treatment group and the estimated difference between the groups and associated 95% confidence intervals and two-sided p-values will be reported. Figures and tables will summarize the outcomes and analysis results.

This analysis will be repeated with the PP population.

Point prevalence abstinence (last 7 days)

One exploratory objective is to evaluate the efficacy of IXT-m200 in improving post-treatment abstinence. Point prevalence abstinence (last 7 days) by saliva screens at Week 25, Week 29, and Week 33 will be compared between each IXT-m200 group and the placebo group.

For each visit of interest, abstinence or use will be based on the saliva screens in the previous seven days. A "use day" or "abstinent day" will be derived as described for the primary endpoint. A participant will be categorized as fully abstinent if their saliva screens are negative (responder); a participant will be categorized as not abstinent if any of their saliva screens are positive (failure). The generalized linear mixed model assumes that data are missing at random.

A generalized linear mixed model regressing binary abstinence on treatment group, visit, stratification level of past-month METH use at screening, and a treatment group by visit interaction term. For each comparison, the odds ratio, 95% confidence interval, and two-sided p-value will be reported. Figures and tables will summarize the outcomes and analysis results. Within-subject correlations will be modeled using an unstructured covariance structure. If the model does not converge (i.e., the study has too few observations for the number of parameters estimated), the model will sequentially use the heterogeneous Toeplitz structure, homogeneous Toeplitz structure, or compound symmetry structure, each requiring successively fewer parameters.

Complete abstinence between Week 21 and Week 25 responder analysis

A secondary objective is to evaluate the efficacy of IXT-m200 in improving the proportion of participants achieving stimulant abstinence, defined as complete abstinence during the last scheduled month of study drug treatment (between Week 21 and Week 25), as measured by saliva screens.

A participant will be categorized as fully abstinent if they have zero days of use (between Week 21 and Week 25); otherwise, a participant will be categorized as not abstinent (failure). Participants who withdraw or discontinue prior to Week 5, or do not have any reported saliva or self-report use data between Weeks 5 and 25 will not be included in the analysis.

The proportion of participants achieving a response will be compared in each IXT-m200 group versus the placebo group using a stratified Mantel-Haenszel statistic with stratification level of past-month METH use at screening (discrete). The output will provide the risk difference between each IXT-m200 dose group and the placebo group, two-sided p-values, and 95% confidence intervals using the Miettinen-Nurminen (score) confidence limits.

Reduction in the frequency of METH use over time

An additional exploratory objective is to evaluate the efficacy of IXT-m200 in reducing the frequency of METH use over time. For each day from the start of Week 5 through the end of Week 25, abstinence or use will be based on the self-reported use in the previous seven days. The number of use days in each week will then be determined.

The weekly total for a subject will be derived by counting the number of use days among the non-missing days and normalizing to a seven-day period. For example, for a subject with 1 use day among 4 non-missing days and 3 missing days in a given week, the number of use days (X) will be derived as X = (1/4)*7 = 1.75. No rounding will be performed. If a subject has all missing days in a given week, that week will not be imputed and therefore will not contribute to the analysis.

The number of use days per week will be summarized in a table presenting the mean and standard deviation for each treatment group, at each of the weeks from 5 to 25. No formal statistical testing will be performed for this endpoint. A plot of these group means across weeks will be provided.

[figure not shown]
A spaghetti plot will also be provided to show the use days per week by subject throughout the study. Pseudo-R code for the plot is included in Exhibit 7, and an example of the plot is included in Exhibit 8.

Exhibit 7 Pseudo-R Code for Weekly Meth Use Days Spaghetti Plot

```
survey$DATE <- as.Date(survey$date)</pre>
startday < -aggregate(DATE \sim SUBJID, survey, function(x) min(x))
